#### General Administration Information:

**Flotetuzumab must not be administered as an IV push or bolus**. During the Cohort Expansion Phase, at least for the first 8 days of Cycle 1 (and after a minimum of 24 hours at the 500 ng/kg/day maximum dose), the drug will be administered in an inpatient hospital setting; but afterwards may be administered in an outpatient setting as described in **Section 4.1.1**. The type of pump used for administration of flotetuzumab may differ by country or region. It is important that at any point, THE INFUSION BAG CONTAINING FLOTETUZUMAB MUST NOT BE SHAKEN; excessive agitation may cause aggregate formation. Subsequent to Cycle 1 Day 8 (and after a minimum of 24 hours at the 500 ng/kg/day maximum dose), patients may, as appropriate (see **Section 6.3**), receive flotetuzumab as a continuous infusion in an outpatient setting using an ambulatory pump configuration. Specific instructions for dose preparation and administration in both the inpatient settings are provided in the Pharmacy Manual.

Sites must ensure patients who receive flotetuzumab in the outpatient setting will be provided instructions and trained appropriately and monitored for compliance and safety.

Flotetuzumab should not be admixed or diluted with other drugs. Any partially used vials or diluted dosing solutions should be discarded using appropriate drug disposal procedures.

#### 6.3 Modification (Including Discontinuation) of Flotetuzumab Dose or Schedule

Interruption or discontinuation of dose or schedule may be necessitated by the observation of suspected drug-associated or drug-related adverse events (AEs). The Investigator should use his/her best medical judgment to intervene in order to safeguard the patient's welfare. The following guidelines should be observed:

In general, observation of any  $\geq$  Grade 3 AE (by CTCAE v4.0), except IRR/CRS which will be by the modified criteria proposed by Lee et al. (26) considered related to flotetuzumab should result in suspension of flotetuzumab study drug administration; for patients in the mini-cohort, ruxolitinib administration should also be suspended. Reinstitution of assigned flotetuzumab study drug administration, and ruxolitinib administration for patients in the mini-cohort, should occur if the AE meets one of the exceptions to the definition of DLT (see Section 4.2). Otherwise, the patient should be withdrawn from further study drug administration unless there are extenuating circumstances, and the Investigator concludes that the patient is continuing to derive clinical benefit.

If after reinstituting flotetuzumab for a first occurrence of  $a \ge Grade 3$  AE (as exempted by the DLT definition), the patient experiences a second (either similar or different)  $\ge$  Grade 3 AE, study drug administration should once again be suspended. As before, reinstitution of any study drug administration should be delayed to see if the AE meets one of the exceptions to the DLT definitions. If so, the Investigator may elect to reinstitute flotetuzumab; patients that have a dosing interruption > 72 hours will reinitiate dosing with a modified multi-step lead-in dose starting at 30 ng/kg/day (followed by steps up to 60, 100, 200, 300, 400, and 500 ng/kg/day) with dose changes every 4-6 hours as tolerated. If the observed AE is associated with autoimmunity, the study drug should be discontinued.

If the second  $\geq$  Grade 3 AE meets the definition of DLT, or a third instance of a  $\geq$  Grade 3 AE occurs, the Investigator should consider the patient to have experienced DLT and the patient should be withdrawn from further study drug administration (see Section 5.4).

Signs and symptoms of active viral infections may overlap with the signs and symptoms of CRS (e.g., fever, hypoxemia). The management of CRS in the setting of active coronavirus infections could theoretically potentially confound the course of the viral infection. The following guidelines apply to participants with confirmed (by a laboratory test) or presumed (test pending/clinical suspicion) SARS-CoV-2 infection:

- Study drug should be stopped in patients who are symptomatic from, or require treatment for, SARS-CoV-2 active infection. The Sponsor, in consultation with the investigator, may permit study drug to be restarted, on a case-by-case basis, if the benefit:risk ratio of continuing therapy with study drug outweighs the benefit:risk ratio of withdrawal from study drug.
- Prior to restarting study drug, when stopped for SARS-CoV-2 infection, participants should be afebrile for at least 72 hours, and SARS-CoV-2–related symptoms should have recovered to ≤ Grade 1 or baseline for a minimum of 48 hours.
- The Sponsor should be informed when restarting flotetuzumab.

When dosing is delayed for  $\geq 24$  hours, continue to follow the Schedule of Events in Appendix 1 and Blood Sampling Schedule in Appendix 2, including on days when no study drug is administered (with the exception of samples for PK, which should not be collected on days when no study drug is administered) or when lead-in dosing escalation is needed to restart flotetuzumab. If a delay of  $\geq 24$  hours during any dosing period occurs, or if less than 75% of the intended dose will be administered if the original schedule is followed, the MacroGenics Medical Monitor should be consulted as to whether the total infusion time should be extended to allow sufficient study drug to be administered.

## 6.4 Special Situations and Supportive Care Measures

## 6.4.1 Infusion-related Reactions including CRS

The predicted mechanism of action of flotetuzumab is the creation of an immunological synapse between the leukemic blast target cell bearing CD123 and immune effectors bearing the T cell specific CD3 complex, leading to T cell activation and killing of the leukemic cell. Activation of T cells is associated with the elaboration of various cytokines. In vitro preclinical testing using human PBMCs has suggested that the most vigorous cytokine production is that of IFN- $\gamma$ , but increases in production of TNF- $\alpha$ , IL-2, IL-6, IL-4, and IL-10 were documented. Cytokine production, primarily of IL-6, was also documented in normal cynomolgus monkeys receiving flotetuzumab - a circumstance in which relatively few target cells (mostly CD123-bearing pDCs) were present in the animal's peripheral blood but elimination of those cells was observed. In the cynomolgus monkey, very high doses of flotetuzumab (i.e., 5 µg/kg/day) were associated with severe cytokine release of multiple cytokines including IL-6, IFN- $\gamma$ , IL-2, TNF- $\alpha$  and to a lesser extent IL-8 and IL-4, resulting in moribundity or death.

#### Infusion-related reactions or Cytokine Release Syndrome (CRS) may occur. Anaphylactic or anaphylactoid-type reactions are possible. Precautions for the management of these reactions should be observed during flotetuzumab administration.

Infusion-related reactions (including CRS) associated with flotetuzumab administration should be managed according to the standard practice of medicine. General guidelines for the management of such reactions are provided in this section. However, severe reactions may require extraordinary interventions like those that have been required to extinguish the syndrome of cytokine storm which may have anaphylactoid features.

Patients should be monitored closely for the development of IRRs during flotetuzumab infusion. Medications and supportive measures for the treatment of such reactions should be available for immediate use for an infusion reaction during study drug administration and may include, but are not limited to: subcutaneous (SC) epinephrine (0.3 to 0.5 mL of a 1:1000 solution), antihistamines (e.g., diphenhydramine 25 to 50 mg IV), corticosteroids (e.g., dexamethasone 10 mg IV push or equivalent), IV fluids, vasopressors, oxygen, bronchodilators, and antipyretics. Resuscitation equipment and other supplies for the emergency management of an allergic/toxic reaction must be available. The patient should be treated according to the best available local practices and procedures. All supportive measures consistent with optimal patient care will be provided throughout the study according to institutional standards.

Should symptoms of fever or chills develop it may be difficult or impossible to distinguish among potential causes of the symptoms including underlying leukemia, neutropenic fever, emerging infection (including SARS-CoV-2), or infusion reaction. Temporarily halting the flotetuzumab infusion to collect cultures, institute antimicrobials, etc., may provide information regarding etiology. If the fever and chills are considered not related (as described in Section 7.11.2) to the infusion of study drug, the study drug may be reinstituted at the

same rate of administration after administration of ibuprofen or acetaminophen and diphenhydramine hydrochloride if not administered previously for premedication. More complex symptom composites may require additional intervention. Please refer to **Section 6.4.1.2** for management of infusion reactions if the event is considered related to flotetuzumab. If during assessment of IRR/CRS a patient undergoes imaging study and/or sample collection, e.g., pleural fluid, intra-articular joint aspiration, or ascitic fluid, a sample may be provided to the Sponsor to help elucidate etiology.

## 6.4.1.1 Premedications and Prophylaxis

Based on the clinical experience to date (Section 2.4), similar findings from other bispecific molecules, such as blinatumomab, reported clinical experience with CAR-T therapies, and after consultation with the study investigators and the prior independent DSM (now replaced by the IDMC), all patients treated in clinical protocol CP-MGD006-01 will receive premedication to prevent or mitigate potential infusion-related reactions. Specific pretreatment regimens are described below. Table 4 presents the premedication and prophylaxis regimens.

Prior to the first dose and during Cycle 1 Week 1, all patients are to be treated as described in **Table 4** below. Patients should receive adequate hydration during study therapy, preferentially oral if tolerated. The addition of IV fluids to maintain intravascular volume (e.g., 50-100 mL/hr of normal saline) is recommended for at least 48 hours after the start of therapy.

For infusion-related reactions during the course of treatment, supportive care measures should be implemented as outlined in **Section 6.4.1**.

#### Dose interruption:

If dosing is interrupted for > 24 hours, the premedication schedule for Week 1 Day 1 should be followed (**Table 4**). If dosing is interrupted twice for > 24 hours, and the patient has no IRR/CRS upon each resumption of dosing, then no premedication is required after the third and subsequent interruptions. Patients that have a dosing interruption > 72 hours will reinitiate dosing with a modified multi-step lead-in dose starting at 30 ng/kg/day (followed by steps up to 60, 100, 200, 300, 400, and 500 ng/kg/day) with dose changes every 4-6 hours as tolerated.

#### Ruxolitinib Cohort (Single Site [Washington University, St. Louis, MO]; up to 12 patients)

#### Treatment Plan:

Up to 12 patients will be treated with prophylactic ruxolitinib and flotetuzumab as follows:

- 1. Ruxolitinib 10 mg PO BID will be administered on Days 0-14 of Cycle 1 of flotetuzumab beginning the day prior to initiation of flotetuzumab.
  - a. Patients in the ruxolitinib cohort should receive all other prophylaxis as indicated in **Table 4**.

- b. Based on cohort interim safety assessment, outlined above, ruxolitinib may be increased to 20 mg twice daily (max recommended dose) (8).
- 2. Flotetuzumab will be administered per the Cycle 1 schedule provided in Table 2.

#### Dose modifications:

Ruxolitinib may be interrupted or reduced to 5 mg BID for suspected ruxolitinib-related adverse events (AEs), i.e., anemia or thrombocytopenia decrease of > 2 Grade decrease while on ruxolitinib.

Mallard	7-day Continuous Infusion Schedule, Cycle 1 Week 1 			
Medication	Day 1	Day 7		
Acetaminophen				
(1000 mg PO)				
Or Paracetamol	30 minutes prior to dosing	30 minutes prior to dose change		
(1000 mg PO) Or	Then q 8 hours for 48 hours	Then q 8 hours for 48 hours		
Ibuprofen (400 mg PO)				
Diphenhydramine	30 minutes prior to dosing	30 minutes prior to dose change		
(25-50 mg IV or PO)				
or equivalent	Then q 8 hours for 48 hours	Then q 8 hours for 48 hours		
Famotidine	30 minutes prior to dosing	30 minutes prior to dose change		
(20 mg IV or PO)				
or equivalent	Then q 8 hours for 48 hours	Then q 8 hours for 48 hours		
	10-20 mg IV	10 mg IV		
	up to 30 minutes prior to dosing	up to 30 minutes prior to dose change		
Dexamethasone (or equivalent)	Then 4 mg IV at 12 hours after dosing	Then 4 mg 12 hours later		
	Then 4–10 mg up to every 8 hours $^{2}$	Then 4–10 mg up to every 8 hours $^{2}$		

Table 4	Premedication and Prophylaxis for Infusion-related Reactions
---------	--

1 If dosing is interrupted for > 24 hours during continuous infusion, the premedication schedule for Week 1 should be followed.

2 Low dose steroids may be administered every 8 hours as clinically indicated to facilitate achievement of the target dose 500 mg/kg.

## 6.4.1.2 Management of Observed Flotetuzumab Infusion Reactions and Infusion-related Adverse Events

The following are treatment guidelines (which may be modified as needed by the responsible Investigator according to the best practices of medicine) for flotetuzumab IRRs including CRS. Early intervention at the first signs of IRR/CRS, including pyrexia, tachycardia, tachypnea and/or hypotension in the absence of alternative etiologies and in consistent temporal relationship to administration of flotetuzumab, should be undertaken. Through Amendment 4, IRR/CRS has been graded using CTCAE v4.0. Based on current understanding gained with patients treated with CAR-T cells (which have a T-cell activating mechanism of action in common with flotetuzumab), CRS is likely to be a common toxicity that can be managed through supportive care and anti-cytokine interventions to allow for full activity of T cells during therapy. An alternative grading scale for CRS proposed by Lee et al. (26) allows for more intensive supportive care and treatment of the underlying cause of the CRS (excessive cytokine production) before the event must be considered Grade 3 or Grade 4 severity. Adopting this definition of CRS as described in Table 5, and concomitantly modifying the guidelines for management of IRR/CRS (below) as implemented in Amendment 5 and further modified in Amendment 13, will allow for more flexible management of patients who develop CRS and who may nonetheless experience clinical benefit despite the need to manage through mild or moderate infusion reactions while not jeopardizing overall safety.

Infusion related reaction including CRS is a common toxicity with flotetuzumab, especially when the drug is initiated and dose escalated during lead-in dosing. Evaluate for and treat other causes of fever, hypoxia, and hypotension according to institutional best practices or guidelines. Initial IRR/CRS management with fluids and antipyretics is allowed as clinically indicated, per local institutional practices. Celecoxib (14), if platelet counts allow, may be considered for myalgia and arthralgia. If celecoxib is contraindicated consider the use of corticosteroids per Table 5, Grade 1 CRS. If CRS is suspected, refer to Table 5 for management guidelines or treat according to local institutional guidance. Every attempt should be made to continue the infusion during management of the reaction. The definitions for high-dose vasopressors are shown in Table 6.

#### Table 5CRS Grading and Recommended Management Guidance

CRS Grade (26)	Dose Modification	Tocilizumab	Corticosteroids
Grade 1 Symptoms are not life threatening and require symptomatic treatment only, e.g., fever, nausea, fatigue, headache, myalgias, malaise	Slow infusion rate by 10-20%. After stabilization/resolution increase infusion rate as clinically indicated every 4-6 hours.	Administer tocilizumab (14) 8 mg/kg IV over 1 hour (not to exceed 800 mg/dose). If no clinical improvement in the signs and symptoms of CRS after the first dose, repeat tocilizumab every 8 hours as needed. Limit to a maximum of 3 doses in a 24-hour period; maximum total of 4 doses.	Administer dexamethasone (e.g., 4 to 6 mg IV or oral every 8 hours) for 24-48 hours.
Grade 2 Symptoms require and respond to moderate intervention Oxygen requirement < 40% or Hypotension responsive to fluids or low-dose of one vasopressor (Table 6) or Grade 2 organ toxicity	Slow infusion rate by 25-50%. After stabilization/resolution increase infusion rate as clinically indicated every 4-6 hours.	Per Grade 1	Manage per Grade 3 if no improvement or worsening within 24 hours after starting tocilizumab.
Grade 3 Symptoms require and respond to aggressive intervention Oxygen requirement ≥ 40% or Hypotension requiring high-dose vasopressors or multiple vasopressors (Table 6) or Grade 3 organ toxicity (except transaminitis) or Grade 4 transaminitis	Interrupt infusion, DO NOT FLUSH line. Aspirate residual drug from line. After resolution or stabilization to Grade 1 resume infusion at previous tolerated dose, and increase rate as clinically indicated every 4-6 hours.	Per Grade 1	Administer dexamethasone (e.g., 8 to 10 mg intravenously every 8 hours) or equivalent. Continue corticosteroid use until the event is Grade 1 or less, then taper over 3 days.

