#### Test Product, Dose, and Mode of Administration:

Patients in Cohort Expansion will receive flotetuzumab as a multi-step-up lead-in dose in Week 1 Cycle 1. This comprises an initial dose of 30 ng/kg/day on Day 1, followed by doses of 60, 100, 200, 300, and 400 ng/kg/day on Days 2, 3, 4, 5, and 6, respectively. On Day 7, the final step up occurs to 500 ng/kg/day (defined as the MTD), given as a continuous infusion through Day 28 of Cycle 1. Throughout subsequent induction and consolidation cycles, dosing continues at 500 ng/kg/day as a 7-day continuous IV infusion each week of a 28-day cycle. Patients that have a dosing interruption > 72 hours will reinitiate dosing with a modified multi-step lead-in dose starting at 30 ng/kg/day (followed by steps up to 60, 100, 200, 300, 400, and 500 ng/kg/day) with dose changes every 4-6 hours as tolerated.

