# 2.3.2.3 Cohort Expansion Segment (Ongoing)

#### **Dosing Modifications**

Implementation of the two-step lead-in dose with Amendment 5 decreased IRR/CRS severity compared to the single-step lead-in dose (20). However, data from a cynomolgus monkey toxicology study revealed that large step-up dose intervals were less well-tolerated than smaller increments (data presented in the flotetuzumab **Investigator's Brochure**). Hence, as of Amendment 8, the lead-in dose was modified from a two-step lead-in dose to a multi-step lead-in dose, comprised of sequential smaller and more frequent dose increments (30 to 60 to 100 to 200 to 300 to 400 to 500 every 24 hours) until reaching the MTD of 500 ng/kg/day. Although more involved, it was anticipated that this more conservative approach to intrapatient dose escalation may further attenuate IRR/CRS.

Prior to Amendment 9, all patients eligible to receive flotetuzumab beyond Cycle 1 received drug on a 4 days on/3 days off schedule in Cycle 2 and beyond. With Amendment 9, dosing was modified to specify 2 treatment phases, "Induction" (up to six 28-day cycles of continuous IV infusion [with multi-step lead-in dosing during Week 1 of Cycle 1] until response criteria were met), followed by "Consolidation" (up to two 28-day cycles of 4 days on/3 days off each week). With Amendment 11 all cycles of flotetuzumab, whether induction or consolidation, will be administered as a continuous infusion in 28 day cycles (see Figure 5 and Section 4.1).

In summary, flotetuzumab is dosed as a continuous infusion based on data from the current trial, and centered around two basic premises. Firstly, in some patients that have not achieved full remission and are treated on intermittent dosing, rebound of peripheral blood AML blasts during the period off flotetuzumab has been observed; secondly, elimination of on-off interruptions in treatment with flotetuzumab may help further limit IRR/CRS.

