## 4.2 **Dose Limiting Toxicity Definitions**

DLT will be defined employing the National Cancer Institute Common Terminology Criteria for Adverse Events, Version 4.0 (CTCAE v4.0), except IRR/CRS which will be defined by the modified criteria proposed by Lee et al. (26) and described in Section 6.4.1.2 and in Table 5. Note: IRR/CRS will be assessed by the grading of the overall IRR/CRS event, and not the grade of component signs or symptoms.

DLT is defined as:

- Grade 4 neutropenia lasting ≥ 42 days from start of cycle in absence of evidence of active AML (< 5% blasts).
- Grade 3–5 nonhematologic toxicity not clearly resulting from the underlying disease and at least possibly related to protocol indicated treatment, EXCEPT:
  - Grade 3 fatigue, asthenia, fever, anorexia, or constipation;
  - Grade 3 nausea, vomiting or diarrhea not requiring tube feeding, total parenteral nutrition, or requiring or prolonging hospitalization, and resolve, with or without intervention, to  $\leq$  Grade 2 levels in < 7 days will not be considered DLT;
  - Infection, bleeding, or other expected direct complication of cytopenias due to active underlying disease;
  - Grade 3 or 4 tumor lysis syndrome (TLS) if it is successfully managed clinically and resolves within 7 days without end-organ damage;
  - Grade 3 or 4 isolated biochemical laboratory abnormalities (i.e., those occurring without clinical consequence) that resolve, with or without intervention, to  $\leq$  Grade 2 levels in < 72 hours will not be considered DLT.
  - Grade 3 rashes, myalgias or arthralgias that resolve within 96 hours and respond to medical intervention.
  - Grade 3 infusion-related reaction or CRS that lasts < 72 hours and responds to medical intervention.
- For patients in the ruxolitinib cohort, an increase of  $\geq 2$  CTCAE v4.0 grades in either hemoglobin or platelet count in patients while on ruxolitinib will also be considered a DLT.
- Any treatment-related death.

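### The Grade 3 CRS row of Table 5 gives a restart dose without the 72-hour limit that the protocol sets elsewhere

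*Protocol*

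**What the plan says.** **The Table 5 row.** For Grade 3 CRS the infusion is stopped, and then: "After resolution or stabilization to Grade 1 resume infusion at previous tolerated dose". The rate is afterwards raised every 4 to 6 hours as clinically indicated. No maximum interruption is given, and neither Section 4.1.1 nor Section 6.3 is mentioned.

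**The general restart rule.** The Synopsis (Test Product, Dose, and Mode of Administration) says: "Patients that have a dosing interruption > 72 hours will reinitiate dosing with a modified multi-step lead-in dose starting at 30 ng/kg/day". The steps are 60, 100, 200, 300, 400 and 500, changed every 4 to 6 hours as tolerated. Section 4.1.1 and Section 6.4.1.1 (Dose interruption) say the same. Section 6.3 repeats it ("patients that have a dosing interruption > 72 hours will reinitiate dosing with a modified multi-step lead-in dose starting at 30 ng/kg/day"), there within the paragraph on a second AE of Grade 3 or higher. None of the four makes an exception for CRS.

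**Who may restart.** Section 4.2 exempts from DLT a "Grade 3 infusion-related reaction or CRS that lasts < 72 hours and responds to medical intervention". Under Section 6.3, reinstitution "should occur if the AE meets one of the exceptions to the definition of DLT". Otherwise "the patient should be withdrawn from further study drug administration unless there are extenuating circumstances" and the Investigator sees continuing benefit.

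**Status of the table.** Section 6.4.1.2 introduces it as guidance "which may be modified as needed by the responsible Investigator according to the best practices of medicine", and also allows treatment according to local institutional guidance.

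**The concern.** The two clocks do not measure the same thing. The DLT exemption looks at how long the Grade 3 reaction lasts. The Table 5 hold runs until Grade 1, so it also includes the time spent at Grade 2. A patient can therefore be exempt from DLT, be due to restart under Section 6.3, and still have been off drug for more than 72 hours. For that patient Table 5 names one starting dose and the general rule names another.

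What is at stake is the starting dose in a patient who has just had Grade 3 CRS. Section 2.3.2.3 explains why the lead-in uses small steps: in a monkey study, "large step-up dose intervals were less well-tolerated than smaller increments". A site that works from the CRS table alone would skip some or all of the lead-in that four other places require.

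**Working it through.** The documents give no statistical figure to reproduce. The check has two parts: whether the instructions can meet in one patient, and how far apart they then are.

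**1. Can both apply without a DLT?** Let G3 be the hours at Grade 3 and G2 the hours at Grade 2 before Grade 1, with the infusion stopped at the onset of Grade 3.

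- Exempt from DLT (Section 4.2): G3 < 72, with response to intervention.
- Length of the Table 5 hold: G3 + G2.
- General restart rule applies: G3 + G2 > 72.

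Both hold whenever G3 < 72 and G2 > 72 − G3. Illustration with assumed durations: G3 = 48 and G2 = 36 give a hold of 48 + 36 = 84 hours, which exceeds 72. With G3 = 48, any G2 above 72 − 48 = 24 hours is enough.

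**2. How far apart are the restart doses?** The lead-in is 30, 60, 100, 200, 300, 400 and 500 ng/kg/day on Days 1 to 7 (Section 4.1.1, Table 2). Assumption: the previous tolerated dose is the step below the dose at the event. Ratio = that step ÷ 30. Time skipped = dose changes skipped × 4 to 6 hours.

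| Day of event | Dose at event | Table 5 restart | Ratio to 30 | Dose changes skipped | Hours skipped |
|---|---|---|---|---|---|
| 2 | 60 | 30 | 30/30 = 1.0 | 0 | 0 |
| 3 | 100 | 60 | 60/30 = 2.0 | 1 | 4–6 |
| 4 | 200 | 100 | 100/30 = 3.3 | 2 | 8–12 |
| 5 | 300 | 200 | 200/30 = 6.7 | 3 | 12–18 |
| 6 | 400 | 300 | 300/30 = 10.0 | 4 | 16–24 |
| 7 | 500 | 400 | 400/30 = 13.3 | 5 | 20–30 |

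A Day 1 event has no earlier dose, so the row gives no answer there. Section 4.1.1 puts peak incidence of IRR/CRS around 48 to 72 hours after the start of dosing. That is Day 3, where the gap is one step. If the row is instead read as allowing a return to 500 in a patient who had already tolerated it, the ratio is 500/30 = 16.7, and all six changes (24 to 36 hours) are skipped.

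**3. How often?** The documents give no rate of Grade 3 CRS followed by an interruption of more than 72 hours, so the number of affected patients cannot be estimated.

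**The case against.** The strongest reply is that the row is silent on length and does not state a contrary rule. The 72-hour rule appears four times in mandatory wording, three of them general, and one of those is in Section 6.4.1.1, shortly before the table. The texts can be read together: previous tolerated dose up to 72 hours, lead-in after that. That is a reasonable reading and may be the intended one. It is not written down, however, and a site could equally take the CRS-specific row as governing.

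These further points stand and limit the weight of the concern:

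- Table 5 is guidance that the Investigator may modify, and local institutional guidance is an allowed alternative.
- CRS of Grade 2 or higher is reported to the sponsor within 24 hours (Sections 7.11.1 and 7.11.3). A delay of 24 hours or more calls for Medical Monitor consultation on infusion time (Section 6.3). Hospitalization for the first 24 to 48 hours of re-initiation (Section 4.1.1) and repeat premedication (Section 6.4.1.1) also apply. None of these sets the restart dose.
- Section 2.3.2.2 reports that patients on the 4 days on/3 days off schedule, reintroduced in Week 2 at 300 or 500 after 100 in week one, had IRR/CRS of the same or lesser severity despite the higher dose. The monkey finding concerns the size of lead-in increments, not a return to a dose already tolerated.

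Three stronger readings are tempting, and the documents do not support them:

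- A reader might infer that the protocol sets no limit on restarting after prolonged Grade 3 CRS. Sections 4.2 and 6.3 do set one. Its absence from the row is a missing cross-reference and no more.
- A reader might infer a special hazard beyond 72 hours because the drug has washed out. Section 7.11.1 puts the half-life at a few hours. Taking 3 to 6 hours as an assumption, five half-lives pass in 15 to 30 hours. A restart at 48 hours, which the general rule permits without lead-in, is then also from almost no drug. Washout does not separate the two cases.
- A reader might take the 13.3-fold gap as typical. It applies to a Day 7 event only.

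**Conclusion.** The concern holds as an unresolved overlap between two dosing instructions. After a DLT-exempt Grade 3 CRS with a hold of more than 72 hours, the row and the general rule give starting doses that differ by a factor of 1 to 13.3 for events on Days 2 to 7, and by a factor of 2 at the stated peak.

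This rests on two readings. First, the previous tolerated dose is taken as the step below the event dose. Second, the 72 hours in the DLT exemption are taken to count time at Grade 3. If they count the whole reaction instead, the overlap narrows mainly to patients kept on drug under the extenuating-circumstances clause of Section 6.3.

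Harm is not established, and no effect on endpoints, alpha or power is claimed. The correction is still worth making, because it concerns the dose given after a serious reaction and costs very little.

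**What to change.** Add the time limit to the Grade 3 row of Table 5. Suggested sense: restart at the last tolerated dose only if the interruption was 72 hours or less; after a longer interruption, any permitted restart uses the modified multi-step lead-in from 30 ng/kg/day in Section 4.1.1. It would help to define the previous tolerated dose in the same place, including what to do after a Day 1 event.

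Pointing the row to Sections 4.2 and 6.3 for the DLT consequence is an optional editorial change.

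The cost is a protocol clarification and a memo to sites, with no additional patients or procedures.
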